# 364 **3.3.3 3-Day Post-Study Safety Contact**

- 365 Study staff will perform a phone call or videoconference with the parent within 3  $(\pm 1)$  days following the
- 8-week final visit. This visit may also be conducted in person at the clinical site. The following willoccur:
- Assessment of adverse events, adverse device effects, and device issues
- Confirmation that participant has successfully transitioned to the desired post-study insulin
   therapy

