# 578 **6.2.3 Hypoglycemic Events**

- 579 Hypoglycemia is only reportable as an adverse event when one of the following criteria is met:
- A hypoglycemic event occurred meeting the following definition of severe hypoglycemia: the 580 event required assistance of another person due to altered consciousness, and required another 581 582 person to actively administer carbohydrate, glucagon, or other resuscitative actions. This means that the participant was impaired cognitively to the point that he/she was unable to treat 583 himself/herself, was unable to verbalize his/ her needs, was incoherent, disoriented, and/or 584 combative, or experienced seizure or loss of consciousness. These episodes may be associated 585 with sufficient neuroglycopenia to induce seizure or loss of consciousness. If glucose 586 measurements are not available during such an event, neurological recovery attributable to the 587 restoration of glucose to normal is considered sufficient evidence that the event was induced by a 588 low glucose concentration. 589
- Evaluation or treatment was obtained at a health care provider facility for an acute event
   involving hypoglycemia, or the participant contacted the site and received guidance following
   the occurrence of an acute event involving hypoglycemia
- Hypoglycemia occurred that was associated with an ADE as defined in section 6.2.1
- Study device discontinued due to hypoglycemia
- 595 When a severe hypoglycemia event occurs (as defined above), a Hypoglycemia CRF should be completed 596 in addition to the Adverse Event CRF. Severe hypoglycemia events should be considered serious adverse 597 events with respect to reporting requirements. When a severe hypoglycemia event occurs during use of a 598 study device, it generally will be considered unrelated to the device (per section 6.2.1) if the device
- functioned as intended and there does not appear to be a flaw in how the device is intended to function.
- 600 6.2.4 Hyperglycemic/Ketotic Events
- 601 Hyperglycemia or ketosis is only reportable as an adverse event when one of the following criteria is met:
- evaluation or treatment was obtained at a health care provider facility for an acute event involving
   hyperglycemia or ketosis, or the participant contacted the site and received guidance on how to
   manage the hyperglycemia/ketosis

- the event involved DKA, as defined by the Diabetes Control and Complications Trial (DCCT) and
   described below

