# 6.2.9 Outcome of Adverse Events

- The outcome of each reportable adverse event will be classified by the investigator as follows:
- 676 RECOVERED/RESOLVED (COMPLETE RECOVERY) The participant recovered from the
   677 AE/SAE without sequelae. Record the AE/SAE stop date.
- RECOVERED/RESOLVED WITH SEQUELAE AE/SAE where the subject recuperated but retained pathological conditions resulting from the prior disease or injury.. Record the AE/SAE stop date.
- FATAL A fatal outcome is defined as the SAE that resulted in death. Only the event that was the cause of death should be reported as fatal. AEs/SAEs that were ongoing at the time of death; however, were not the cause of death, will be recorded as "resolved" at the time of death.
- ONGOING (NOT RECOVERED/NOT RESOLVED) An ongoing AE/SAE is defined as an ongoing event with an undetermined outcome.

- An ongoing outcome will require follow-up by the site in order to determine the final outcome of the AE/SAE.
- The outcome of an ongoing event at the time of death that was not the cause of death, will be
  updated and recorded as "resolved" with the date of death recorded as the stop date.
- ONGOING (MEDICALLY STABLE) AE/SAE is ongoing, but medically stable. For example,
   a chronic condition where no further change is expected.

692 If any reported adverse events are ongoing when a participant completes the study (or withdraws),

adverse events classified as UADEs or related SAEs will be followed until they are either resolved, or have no prospect of improvement or change, even after the participant has completed all applicable study visits/contacts. For all other adverse events, data collection will end at the time the participant completes the study. Note: participants should continue to receive appropriate medical care for an adverse event after their participation in the study ends.

If a participant is lost to follow up and participant outcome cannot be determined, outcome classificationwill be the last known outcome.

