# 6.6.1 Participant Discontinuation of Study Device

In the case of an unanticipated system malfunction resulting in a severe hypoglycemia or DKA event (or a

- malfunction that could have led to severe hypoglycemia or DKA), use of the study device will be
- suspended while the problem is diagnosed. The UADE will be reported to the IRB, DSMB, and FDA.
- After assessment of the problem and any correction, use of the study device will not be restarted until approval is received from the IPP DSMP and EDA
- approval is received from the IRB, DSMB, and FDA.
- In the absence of a device malfunction, use of the study device by a participant will be discontinued if any
   of the following occur and the participant will be withdrawn from the study:
- The investigator believes it is unsafe for the participant to continue on the intervention. *This could be due to the development of a new medical condition or worsening of an existing condition; or participant behavior contrary to the indications for use of the device that imposes on the participant's safety*

- The participant requests that the treatment be stopped
- Two distinct episodes of DKA as defined in section 6.2.4
- Two distinct severe hypoglycemia events as defined in section 6.2.3
- One episode of DKA as defined in section 6.2.4 and one severe hypoglycemia event as defined in section 6.2.3

Each DKA or severe hypoglycemia event will be reviewed by the Medical Monitor and by the DSMB

with respect to determination of cause and whether the occurrence of the event can be attributed to use of the study device.

An additional requirement for continued study device use following a single DKA or severe

780 hypoglycemia event will be that the site investigator believes that the event is unlikely to recur and that it

is safe for the participant to continue to use the system. Additionally, if either the Medical Monitor or

- DSMB determines that the occurrence of the event indicates that it is not safe for the participant to
- continue to use the study device, use will be discontinued.

786

Even if the study device system is discontinued, the participant will be encouraged to remain in the study through the final study visit.

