#### 908 Exploratory Endpoints

| 909               | • Insulin   |  |  |
|-------------------|---|--|--|
| 910               | 0   | Total daily basal insulin (units/kg)   |  |
| 911               | 0   | Total daily bolus insulin (units/kg)   |  |
| 912               | 0   | Total daily manual bolus (units/kg)  |  |
| 913               | 0   | Total daily automated bolus (units/kg)   |  |
| 914               | 0   | Number of manual insulin doses per day   |  |
| 915               | 0   | Number of manual insulin doses with carb announcement per day                            |  |
| 916               | 0   | Average daily profile basal rate divided by total daily insulin in percentage points     |  |
| 917               | 0   | Average carbohydrate ratio daily profile (C:I) multiplied by total daily insulin         |  |
| 918               | 0   | Average insulin sensitivity factor daily profile (G:I) multiplied by total daily insulin |  |
| 919               |   | 8.5 Analysis Datasets and Sensitivity Analyses   |  |
| 920
921
922 | To be included in included in analyses of CGM and insulin outcomes, participants must provide at least 168 hours of CGM data for each of the baseline and trial phase and spend at least 50% of the study period in closed-loop mode. |  |  |

923 All participants who enroll in the PEDAP-AI study will be included in the safety analyses of endpoints

that are not measured by CGM. Analyses will include all events that occur between enrollment and the 3-924

Day Post-Study Safety contact or the end of the 71st day after the date of the Closed Loop Initiation 925

visit—whichever is earlier. For participants who do not complete the study, the date of the final contact 926 927

will be used in place of the 3-Day Post-Study Safety contact date.

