- 200 the second 4-weekperiod will be the end of the day before the 8-Week visit dateor the end of the 59th day
- after the date of the Closed Loop Initiation visit- which ever is earlier. This date will also serve as the end
- 202 of the sixth adaptation period, which will begin at the 6-Week visit. The other five adaptation periods will 203 include data from the adjustment of pump settings at the visit until the adjustment of pump settings at the
- subsequent visit. If the subsequent visit is missed or out-of-window, the end of the period will be the end
- of the day on the latest date that would be in-window for the visit. If a participant misses a vi, sit they will
- 206 be absent from the period begun by that visit. Participants must provide CGM data for at least 75% of the
- 207 time period to be included in the plots and tabulations for that time period.
- 208 7 Safe ty Analyses
- 209 Hierarchical safety endpoints will be analyzed according to the directions in 6.1. All safety endpoints
- 210 listed in 5.1 will be summarized in tables. Details of each reportable adverse event will be provided in a
- 211 listing.

212 8 Intervention Adherence

- 213 The following will be tabulated for the 8-weekstudy period to assess intervention adherence:
- PercenttimeofCGMsensoruse
- Percent time of closed-loop system use
- Percent time in different operational modes
- Percent of Al recommendations that are accepted without any study physician adjustments
- 218
- o For Al recommendations that are adjusted, tabulation of initial and adjusted values

219 System use metrics will be calculated from the beginning of study pump useuntil the end of the day

before the 8-Week visit date or the end of the 59th day after the date of the Closed Loop Initiation visit-

whichever is earlier. For participants who do not complete the study these metrics will be prorated: the

date of the final contact will be used in place of the 8-Week visit date.

223 9 Protocol Adherence and Retention

- 224 The following tabulations and analyses **will** be performed to assess protocol adherence for the study:
- Number of protocol and procedural deviations
- Flowchart accounting for all enrolled participants
- Flowchart of all participants at all scheduled visits and phone contacts after treatment initiation
- Number of and reasons for unscheduled visits and phone calls

JAEBCENTER FORHEALTH RESEARCH

- Number of participants who stopped treabnent and reasons

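### Protocol 6.6.1 orders withdrawal of a child taken off the device for a listed reason, yet ends by encouraging that child to stay, so safety follow-up after a stop is not assured

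*Protocol*

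**What the plan says.** Protocol 6.6.1 deals first with malfunctions. It then says that, without a malfunction, device use stops if any "of the following occur and the participant will be withdrawn from the study". The five reasons are: the investigator judges continued use unsafe, a request to stop, two DKA episodes, two severe hypoglycemia events, or one of each. A later paragraph lets the Medical Monitor or the DSMB stop device use after a single event and does not mention withdrawal. The section ends: "Even if the study device system is discontinued, the participant will be encouraged to remain in the study through the final study visit".

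The effects of withdrawal are set elsewhere:

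- Protocol 7.8 uses a withdrawn participant's data only up to the time of withdrawal.
- Protocol 8.5 and SAP 5.3 normally close the window for safety events not measured by CGM at the 3-day post-study contact, or at day 71 if that is earlier. "For participants who do not complete the study, the date of the final contact" takes the place of that contact.
- Protocol 6.2.9 continues to follow ongoing UADEs and related SAEs after a child completes or withdraws. "For all other adverse events, data collection will end at the time the participant completes the study".
- Protocol 3.3.3 places the following at the 3-day post-study contact, after the 8-week visit: "Confirmation that participant has successfully transitioned to the desired post-study insulin" therapy.

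**The concern.** The two sentences in 6.6.1 give opposite instructions for the same child. A site that reads the first ends the child's participation. A site that reads the last keeps the child to week 8. Each can point to the current text.

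Protocol 8.2 makes safety the primary outcome, and 8.4.1 lists severe hypoglycemia and DKA events and their rates per 100 person-years. The participants are aged 2 to under 6. A child who has just had two such events and is being moved to another insulin regimen is one whose next few weeks a safety study would want to see. Under the withdrawal clause, any new event after the final contact falls outside the window, and no stated step replaces the check that the change of therapy went well.

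**Working it through.** The documents give no figure on this point, so there is none to reproduce. The check sets the provisions side by side and then sizes the loss.

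**Is there a conflict?** The withdrawal clause covers all five reasons. The closing sentence covers any discontinuation of the device and names no exception. The texts agree only if the closing sentence is confined to malfunctions or to single-event stops by the Medical Monitor or DSMB. The section does not say so. That reading would also follow a child stopped after one DKA to week 8, but end follow-up of a child with two.

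**Does the exception in 6.2.9 fill the gap?** Only in part. It covers ongoing UADEs and related SAEs, not new events. The five reasons apply without a malfunction, and 6.2.3 says of a severe hypoglycemia event during use of a "study device, it generally will be considered unrelated to the device (per section 6.2.1) if the device" worked as intended and its design shows no flaw. Section 6.2.4 says the same of DKA. Many triggering events would therefore not qualify for continued follow-up.

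**Size for one child.** Inputs: 8 weeks = 56 days plus the 3-day contact, giving 59 days from the start of study pump use on target dates; 7 contacts after initiation (Table 4-1); 30 planned completers (8.3). Assumption: the final contact is on the stop day d. Days lost = 59 − d. Share of all planned observation = (59 − d) / (30 × 59) = (59 − d) / 1,770.

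| Stop day | Days lost | Share of the child's 59 days | Share of 1,770 child-days | Contacts still to come |
|---|---|---|---|---|
| 14 | 45 | 76% | 2.5% | 4 of 7 |
| 28 | 31 | 53% | 1.8% | 3 of 7 |
| 42 | 17 | 29% | 1.0% | 2 of 7 |

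Any contact after the stop shortens these losses, so they are upper bounds on the target schedule.

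**Effect on the event rate.** Full follow-up gives 30 × 59 / 365.25 = 4.85 person-years, so one event adds 100 / 4.85 = 20.6 per 100 person-years. The documents give no event rate, so a simulation over assumed rates cut each child's follow-up at the second event:

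| Assumed true rate per 100 person-years | Rate obtained, equal risk | Rate obtained, risk concentrated in a few children (gamma shape 0.1) | Chance that any of 30 children has two events |
|---|---|---|---|
| 10 | 10.1 | 9.8 | 0.4% to 3.3% |
| 50 | 49.9 | 45.3 | 9% to 37% |
| 100 | 100.0 | 80.1 | 30% to 66% |

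The pooled rate is close to the truth unless events are both frequent and clustered.

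**The case against.** The best defence is that the section can be reconciled. The withdrawal clause is specific and mandatory, while the closing sentence is general and directly follows the paragraph on single-event stops. On that view, a site that keeps a child after two DKA episodes departs from an express instruction. The reading is possible, but it has to be supplied by the reader, and the difference it creates between one event and two has no evident safety rationale.

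A second defence is that the objective concerns initiation and use of the closed-loop system, so events after the device is off are of less interest in a pilot that is not formally powered. That is a fair argument about priority. It does not explain why the section encourages the child to stay, and it does not cover the change of therapy, which the study itself sets in motion. The relatedness wording is also only a general presumption: the Medical Monitor and DSMB review each DKA or severe hypoglycemia event.

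Three stronger readings are tempting, and the documents do not support them.

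- A reader might infer that withdrawal falls on the children with the most safety events. Investigator judgment and a request to stop need involve no event at all.
- A reader might infer that the SH and DKA rates are seriously biased. The triggering events are counted whichever sentence is followed, and the simulation shows a material effect only under assumed high and clustered rates.
- A reader might infer that the conflict decides the CGM non-inferiority tests, because 8.5 requires children to "spend at least 50% of the study period in closed-loop mode" and SAP 8 states: "For participants who do not complete the study these metrics will be prorated: the" final contact date is substituted. That sentence belongs to the adherence tabulations, and neither document applies it to the inclusion rule. If the period is a fixed 8 weeks, a child stopped before day 28 is below 28/56 = 50% whether withdrawn or not. The documents give no SD for the changes, and the hierarchical analysis section refers to robust methods for skewed changes, so no effect on those tests can be shown.

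**Conclusion.** The contradiction in 6.6.1 is real and stands in the current protocol text. Its consequence is conditional. If the withdrawal clause is followed, collection of new adverse events ends at the final contact, and the contact confirming a safe change of insulin therapy is not assured, including for children who have just had repeat DKA or severe hypoglycemia.

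For an affected child the loss may be large, up to 45 of 59 days for a stop at day 14 with no later contact. For the study as a whole it is likely to be small: one such child is at most 2.5% of planned observation, and few children are likely to be affected. The point is worth correcting for the care and follow-up of individual children and for consistency between sites. It does not threaten the planned analyses. The day counts assume target visit dates and a final contact on the stop day. The simulated rates rest on assumed event rates and clustering.

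**What to change.** In Protocol 6.6.1, delete the clause ordering withdrawal from the sentence that introduces the five reasons. Device use then stops, and the closing sentence governs: the child is followed to the 8-week visit and the 3-day safety contact unless the parent withdraws consent. A request to stop treatment should not by itself be taken as withdrawal of consent. The closing sentence names only the final visit, so adding the 3-day contact there would remove any doubt.

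The event window in Protocol 8.5 and SAP 5.3 needs no change, because a child who stays reaches the 3-day contact in the ordinary way. No change to the CGM analyses is needed for this point. In particular, a fixed 56-day denominator for the closed-loop rule would exclude every child stopped before day 28 from both CGM safety tests.

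The cost is one deleted clause and, for a few children, contacts already in Table 4-1: at most four for a stop at the 2-week visit, all of which may be remote. Parents keep the right to withdraw at any time.

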## 6.6.2 Criteria for Suspending or Stopping Overall Study

787 In addition to the suspension of device use due to a UADE as described in section 6.2.1, study activities

could be similarly suspended if the Medical Monitor deems suspension of study activities or stoppage of

the study necessary based on the totality of safety data available or if the manufacturer of any constituent study device requires stoppage of device use for safety reasons (e.g., product recall). The affected study

study device requires stoppage of device use for safety reasons (e.g., product recall). The affected study activities may resume if the underlying problem can be corrected by a protocol or system modification

that will not invalidate the results obtained prior to suspension.

# 793 Chapter 7: Miscellaneous Considerations

# 794 **7.1 Drugs Used as Part of the Protocol**

Participants will use standard care lispro or aspart rapid-acting insulin prescribed by their personalphysician.

# 7.2 Collection of Medical Conditions and Medications

*Pre-Existing Condition:* Any medical condition that is either present at screening, a chronic disease, or a
 prior condition that could impact the participant's health during the course of the study (e.g., prior
 myocardial infarction or stroke).

801 Medical Conditions During the Study: In addition to conditions meeting the reporting requirements for an

adverse event or device issue as described above, the following medical conditions should also be
reported: (1) new diagnosis of a chronic disease (i.e., not present at the time of enrollment), (2) worsening
of an existing condition, and (3) any medical condition that could affect the participant's ability to carry

805 out any aspect of the protocol or could affect an outcome assessment.

806 *Medications:* All medication for the treatment of chronic pre-existing conditions, medical conditions

(including medical conditions that do not require recording), and/or adverse events that the participant is

currently taking at screening and during the course of the study should be recorded. Nutraceuticals and

preventative treatment also should be recorded. Medications only taken as needed either can be recorded

810 when prescribed or only recorded if used during the study. Glucagon for treatment of severe

811 hypoglycemia will only be recorded if used during the study.

812

821

797

# 7.3 Prohibited Medications, Devices, Treatments, and Procedures

Participants using an insulin not approved for the study pump at the time of enrollment will be asked to contact their personal physician to change their prescribed personal insulin to lispro or aspart for the

815 duration of the trial.

Treatment with any non-insulin glucose-lowering agent (including GLP-1 agonists, Symlin, DPP-4 inhibitors, SGLT-2 inhibitors, biguanides, sulfonylureas and naturaceuticals) will not be permitted.

818 The body-worn study devices (t:slim X2 insulin pump, study CGM systems) must be removed before

819 Magnetic Resonance Imaging (MRI), Computed Tomography (CT) or diathermy treatment. Participants

820 may continue in the trial after temporarily discontinuing use if requiring one of the treatments above.

# 7.4 Precautionary Medications, Treatments, and Procedures

822 Not applicable.

# 823 **7.5 Prophylactic Medications, Treatments, and Procedures**

Not applicable.

